## 8.7.3. Vital Signs Parameters

All vital signs parameters, with changes from baseline will be listed; any value outside the clinical reference range will be flagged.

Summary tables and boxplots by treatment and timepoint will be provided for all vital signs parameters with changes from baseline.

## 8.7.4. 12-lead Electrocardiogram Parameters

All 12-lead ECG parameters, with changes from baseline will be listed; any value outside the clinical reference range will be flagged.

Summary tables and boxplots by treatment and timepoint will be provided for all 12-lead ECG parameters, with changes from baseline.

An outlier analysis will be performed for QT interval corrected for heart rate using Bazett's formula (QTcB) and QT interval corrected for heart rate using Fridericia's formula (QTcF). The analysis will include all individual original, repeat, and unscheduled postdose values.

The maximum postdose values will be summarized by treatment according to the following categories:

- ≤450 ms
- >450 and \( \le 480 \) ms (all instances flagged in the listing)
- >480 and \le 500 ms (all instances flagged in the listing)
- >500 ms (all instances flagged in the listing)

The maximum increases from baseline will be summarized by treatment according to the following categories:

- <30 ms
- >30 and  $\le 60$  ms (all instances flagged in the listing)
- >60 ms (all instances flagged in the listing)

#### 8.7.5. Heat Pain Threshold and Tolerance Tests

Heat pain threshold and tolerance level tests will be conducted using a computer-controlled thermal sensory analyzer device on the subject's thigh.

For the heat pain threshold and heat pain tolerance tests, each test will be performed 3 times at each scheduled timepoint and the computer will record the mean time recording from the 3 experiments for that timepoint.

All heat pain threshold and tolerance tests data, with changes from baseline will be listed.

Summary tables by treatment and timepoint will be provided for heat pain threshold and tolerance tests data, with changes from baseline.

## 8.7.6. Injection Site Assessments

Injection site assessments will involve evaluation of the dosing site for the following criteria:

• Pain will be evaluated according to the following scale:

Grade 0	Grade 1	Grade 2	Grade 3	Grade 4
None	Does not	Interferes with	Prevents daily	Requires
	interfere with	activity or	activity or	medical
	activity	repeated use of	repeated use of	intervention
		non-narcotic	narcotic pain	greater than
		pain reliever	reliever	analgesia

• Redness will be assessed by estimating the size of the red patch at the injection site across its widest point, and will be evaluated according to the following scale:

Grade 0	Grade 1	Grade 2	Grade 3	Grade 4
0-24 mm	25-50 mm	51-100 mm	More than	Requires
			100 mm	medical
				intervention
				greater than
				analgesia

• Swelling will be assessed by estimating the size of the raised area around the injection site across its widest point, and will be evaluated according to the following scale:

Grade 0	Grade 1	Grade 2	Grade 3	Grade 4
0-24 mm	25-50 mm and	51-100 mm or	More than	Requires
	does not	interferes with	100 mm and	medical
	interfere with	activity	prevents daily	intervention
	activity	-	activity	greater than
				analgesia

In addition, how the swelling affects the subject in their daily routing activities will be considered.

• Tenderness will be evaluated using the following scale:

Grade 0	Grade 1	Grade 2	Grade 3	Grade 4
None	Mild pain to	Moderate Pain	Severe pain to	Requires
	touch	to touch	touch	medical
				intervention
				greater than
				analgesia

• Bruising and ulceration will be evaluated as being present or absent

Local tolerability ratings of ≥Grade 3 and the presence of ulceration will be recorded as an AE.

All injection site assessment data will be listed.

Summary tables by treatment and timepoint will be provided for injection site assessment data.

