#### 3. STUDY ENDPOINTS

## 3.1. Primary Endpoints

The primary safety endpoints for this study are as follows:

- incidence and severity of adverse events (AEs)
- vital signs measurements (blood pressure, pulse rate, respiratory rate)
- 12-lead electrocardiogram (ECG) parameters

• incidence of clinical laboratory abnormalities, based on clinical chemistry, hematology, and urinalysis test results

- physical examinations
- injection site assessment
- demonstrate that exposure to OLP-1002 does not exceed pre-defined exposure limits from non-clinical studies.

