#### 4.1. Part A

Part A will comprise a single-dose, sequential-group design. Overall, 68 healthy subjects will be studied in 11 groups.

Potential subjects will be screened to assess their eligibility to enter the study within 28 days prior to the first dose administration. Potential subjects for Groups A2, A4, A6, A9, A10, and All will attend a pre-screening visit for an intradermal capsaicin test.

Each subject will participate in 1 treatment period only, and will reside at the Clinical Research Unit (CRU) from Day -2 (2 days before dosing) to Day 3. All subjects will return for non-residential visits on Days 4, 7 (±2 days), 10 (±2 days), and 14 (±2 days), and for a poststudy visit on Day 28 (±2 days).

Based on the ongoing review of the safety and tolerability, additional non-residential visits may be required. The number of additional visits per subject will not exceed 3 and will not extend beyond Day 28 (±2 days).

Doses will be administered in an escalating manner following satisfactory review of safety and tolerability data up to Day 10 (216 hours postdose) from the lower dose levels. For doses ≥12 µg, PK data will also be reviewed up to Day 7 prior to dose escalation.

In Part A, Groups A1, A3, A5, A7, and A8 will consist of 4 subjects; 3 subjects will receive OLP-1002 and 1 subject will receive placebo. To assess PD parameters, Groups A2, A4, A6, A9, A10, and A11 will consist of 8 subjects; 6 subjects will receive OLP-1002 and 2 subjects will receive placebo.

Sentinel dosing will be employed for all groups in Part A. To maintain the blind in a 4-subject group, the first subject will be dosed 48 hours before the second subject, and the second subject will be dosed 48 hours prior to the third and fourth subjects. In PD assessment groups, 2 subjects (1 active: 1 placebo) will be dosed 48 hours before the remaining 6 subjects (5 active: 1 placebo).

The total duration of study participation for each subject (from Screening through Follow-up visit) is anticipated to be approximately 8 weeks.

A schematic of the study design is presented in Figure 1.

Figure 1: Study Design (Part A)

Active = OLP-1002; SC = subcutaneous 6 groups consist of 8 subjects (6 active: 2 placebo); all other groups will consist of 4 subjects (3 active: 1 placebo).

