## 8.1.3. Repeat and Unscheduled Readings

For vital signs and ECG data only, any predose value recorded in addition to the original value or a postdose value recorded within 15 minutes of the original value will be defined as a repeat value; any postdose value recorded more than 15 minutes after the original value will be defined as an unscheduled value. For all other data types (eg, laboratory parameters), any value recorded in addition to the original value will be defined as an unscheduled value.

The original value will be replaced by the last associated repeat value in all calculations, with the exception of the ECG outlier analysis (see Section 8.7.4).

As unscheduled values are not associated with any scheduled timepoint, they will be excluded from all calculations, with the exception of the baseline derivation (see Section 8.1.4) and ECG outlier analysis (see Section 10.7.4).

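### The SAP specifies no subject-level (any-time or worst-grade) summary of injection-site reactions by dose, so below Grade 3 the number of subjects affected must be counted by hand from listings

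*SAP*

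**What the plan says.** SAP section 3.1 includes "injection site assessment" among the primary safety endpoints. Section 8.7.6 grades pain, redness, swelling and tenderness from 0 to 4 and records bruising and ulceration as present or absent. It plans two outputs:

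- a listing: "All injection site assessment data will be listed";
- a summary: "Summary tables by treatment and timepoint will be provided for injection site assessment data".

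The same section sets the link to adverse events: "Local tolerability ratings of ≥Grade 3 and the presence of ulceration will be recorded as an AE". Section 8.7.1 counts subjects with TEAEs by preferred term and treatment. Repeated events with one preferred term count once, at maximum severity.

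Section 8.1.3 deals with extra values. For data other than vital signs and ECG, "any value recorded in addition to the original value will be defined as an unscheduled value". It continues: "As unscheduled values are not associated with any scheduled timepoint, they will be excluded from all calculations". The only exceptions are the baseline derivation and the ECG outlier analysis. Section 8.1.1 keeps early-termination data out of summary statistics, in a rule placed under continuous data. Section 4.1 allows additional visits in Part A after ongoing review of safety and tolerability: "The number of additional visits per subject will not exceed 3".

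**The concern.** A local reaction appears, peaks and fades at different times in different subjects. The usual tolerability question for a subcutaneous product is how many subjects at each dose had a reaction, and what each subject's worst grade was. A table by timepoint answers a different question, namely how many were affected at each scheduled look. Its rows cannot be added, because one subject may appear in several rows and different subjects may fill different rows. Part B adds to this, because each subject receives five doses and reactions may recur or first appear at any of them.

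The TEAE tables fill the gap only for what must be recorded as an adverse event. Grade 1 and 2 ratings and bruising fall below that trigger. Grade 2 pain already means interference with activity or repeated use of a non-narcotic pain reliever, so the part left without a subject-level summary is not trivial. The consequence is that a dose trend in mild or moderate local reactions would be harder to see in the planned tables of a primary endpoint.

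**Working it through.** **Denominators, from section 4.** Part A has 5 groups of 4 and 6 groups of 8: 5 × 4 + 6 × 8 = 68, which reproduces the stated total. Active subjects number 5 × 3 + 6 × 6 = 51 and placebo subjects 5 × 1 + 6 × 2 = 17. Each Part A dose level therefore has 3 or 6 active subjects. Groups B1 to B4 each have 6 active and 2 placebo.

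**What timepoint counts determine.** Let n be the number of subjects at a dose and c_t the number with a given finding at timepoint t, for example Grade 1-2 redness. The number ever affected is the size of the union of the subjects counted at each timepoint, so

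max(c_t) ≤ number ever affected ≤ min(n, Σ c_t).

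The lower limit applies when the same subjects recur. The upper limit applies when each timepoint contributes different subjects. The same bound applies to the number reaching any chosen grade or worse, and so to worst grade.

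**Illustration.** The SAP does not give the injection-site assessment schedule, which may properly sit in the protocol. The timepoints and counts below are assumptions.

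| Active n | Affected per timepoint | Timepoints (assumed) | Lower limit | Upper limit |
|---|---|---|---|---|
| 6 | 1 | 3 | 1/6 = 17% | min(6, 3)/6 = 50% |
| 6 | 1 | 5 | 1/6 = 17% | min(6, 5)/6 = 83% |
| 3 | 1 | 3 | 1/3 = 33% | min(3, 3)/3 = 100% |

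**Which output holds which finding.**

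| Finding | Listing | Timepoint table | Subject-level table |
|---|---|---|---|
| Grade 3 or higher, or ulceration | yes | yes, if at a scheduled timepoint | yes, through the TEAE tables |
| Grade 1-2 or bruising, scheduled timepoint | yes | yes | none specified |
| Grade 1-2 or bruising, unscheduled | yes | no (8.1.3) | none specified |

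**Additional Part A visits.** Section 8.1.3 defines an unscheduled value as one additional to the original and does not name these visits. Its stated reason, that such values belong to no scheduled timepoint, fits them. Exclusion is therefore the likely reading of any injection-site finding made there, but it is an inference.

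**Comparison within the SAP.** Section 8.7.4 summarizes maximum postdose QTc by treatment, using original, repeat and unscheduled values. Section 8.7.1 counts repeated TEAEs once, at maximum severity. Injection-site grades are ordinal and primary, and section 8.7.6 gives them neither treatment.

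**The case against.** The strongest reply is that nothing is lost. All injection-site data are listed, without restriction to scheduled timepoints. With 3 or 6 active subjects per dose, a reader can count the subjects affected and find each worst grade. Reactions at or above the adverse-event trigger already have subject-level counts. That trigger is also a floor, because it says what must be an adverse event and does not bar lower grades. Section 1 places detailed table layouts in the TFL shells, which are not at hand and could contain a worst-grade row. Section 3.1 speaks of incidence for adverse events and laboratory abnormalities but not for injection sites, and the study is descriptive.

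Much of this stands. A reader might infer that Grade 1-2 reactions are never reported; the listing rules that out. A reader might also infer that the tables understate mild and moderate intolerance because they omit visits prompted by a reaction. The SAP does not support that: it does not say that injection sites are assessed at the additional visits, or that those visits answer an individual subject's reaction, and it provides for them in Part A only. A range of 17% to 100% for a 6-active group would need at least six timepoints with one affected subject at each, and the SAP gives no such schedule.

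What the reply does not remove is that a listing is not a prespecified summary. The hand count would run over several criteria, many timepoints, up to 11 Part A dose levels and a pooled placebo group, with no stated rule on whether unscheduled values count. Lower grades may be entered as adverse events, but section 8.7.6 does not require it, so the TEAE tables cannot be relied on for that number.

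**Conclusion.** The point holds as a gap in how a primary safety endpoint is summarized; the data themselves are reported. The SAP text specifies no table of subjects with any injection-site reaction, or of worst grade, by dose. For Grade 1-2 reactions and bruising, the planned timepoint table only bounds that number, and the exact count must come from the listings. Grade 3 or higher ratings and ulceration are covered.

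The size depends on the data and the assessment schedule. The 17% to 50% range for 6 active subjects assumes three timepoints with one affected subject at each, and other patterns give narrower or wider limits. The exclusion of findings at the additional Part A visits is probable but not stated. The conclusion also assumes that the TFL shells hold no such table. If they do, one confirming sentence in section 8.7.6 closes most of the point, leaving only the rule on unscheduled and early-termination values. No figure in the SAP changes. This is a worthwhile, inexpensive improvement.

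**What to change.** - **Section 8.7.6:** add a table by treatment of the number of subjects by worst postdose grade for pain, tenderness, redness and swelling, and the number with any bruising or any ulceration. Take the worst value over scheduled, unscheduled and early-termination assessments. For Part B, show it overall and by dose number. Keep the timepoint table for the time course.
- **Section 8.1.3:** name this table as an exception to the exclusion of unscheduled values, beside the ECG outlier analysis, and say whether findings at the additional Part A visits count as unscheduled.
- **Section 8.1.1:** state the matching exception to the early-termination rule. Inclusion of unscheduled values follows the QTc convention in section 8.7.4; inclusion of early-termination values goes one step beyond what that section states.

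The cost is one extra summary table (with its Part B breakdown) and two short exemptions. It uses data already collected and needs no new procedure.

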## 8.7.7. Other Assessments

All other safety and tolerability assessments not detailed in the above sections will be listed only.

Medical history will not be listed.

## 8.7.8. Safety and Tolerability Statistical Methodology

No inferential statistical analyses are planned.

**CONFIDENTIAL** 

#### 9. INTERIM ANALYSES

In Part A, doses will be administered in an escalating manner following satisfactory review by the Sponsor and Investigator of the safety, and tolerability data up to Day 10 (216 hours postdose) from groups that received lower doses of OLP-1002. For escalation to doses ≥12 µg, PK data up to Day 7 (144 hours postdose) will also be reviewed. All available safety, tolerability, and PK data from previous groups will be reviewed prior to dose escalation.

In Part B, doses will be administered in an escalating manner following satisfactory review of safety, tolerability, and PK data up to Day 22 (216 hours post-final dose) from groups that received lower doses of OLP-1002. Doses may be reduced and may be lower than the starting dose. Available safety, tolerability, and PK data from all previous groups will be reviewed prior to dose escalation.

Dose escalation in Part A will only occur if data from a minimum of 4 subjects (Groups A1, A3, A5, A7, and A8) or 6 subjects (Groups A2, A4, A6, A9, A10, and A11) have been reviewed from the previous lower dose group, such that data from a minimum of 3 or 4 subjects, respectively, who have received OLP-1002 will be used to make the dose-escalation decision. Dose escalation in Part B will only occur if data from a minimum of 6 subjects have been reviewed from the previous lower dose group, such that data from a minimum of 4 subjects who have received OLP-1002 will be used to make the dose-escalation decision.

The justification for this is as follows:

- The study drug is of a known pharmacological class for which the on-target effects in humans are well characterized. Based upon nonclinical data, no clinically important off-target effects are expected within the proposed dose range.
- A minimum of 3 subjects receiving the active drug is considered sufficient to characterize the safety profile for OLP-1002.

Between each dose escalation, the Investigator will review all available blinded data to ensure it is safe to proceed with the planned dose escalation. An interim safety report, summarizing results from all available safety assessments, will be sent to the Sponsor and a dose-escalation meeting will occur prior to the start of each successive group. Any clinically significant results will be discussed with the Sponsor before dose escalation continues. Interim PD data may also be reviewed on an ongoing basis. In the event of a disagreement between Sponsor and Investigator on the dose-escalation decision, the decision of the Investigator will be upheld.

#### 10. SIGNIFICANT CHANGES FROM THE PROTOCOL-SPECIFIED ANALYSES

There were no significant changes from the protocol-specified analyses.

## 12. APPENDICES

# **Appendix 1: Document History**

Version, Status	Date of Change	Summary/Reason for Change	
Version 1, Final	NA	NA; the first version.	

NA = not applicable

